#### Safety Profile of Lapatinib

Preliminary serious adverse events (SAE) data are available for ongoing lapatinib studies (all phases) up to a cut-off date of 22 June 2005. At the time of the SAE cut-off, over 3109 subjects have received lapatinib in phase I, II and III studies. A total of 2620 SAEs were reported from 543 individual subjects. The most frequently reported SAE was diarrhoea, with a total of 123 reports, 66 of which were assessed as related to investigational product. Pyrexia, dyspnoea, vomiting and nausea were also amongst the most frequently reported SAEs regardless of relatedness. Overall, 32% of the SAEs reported were assessed as related to investigational product by the investigator. The majority (81%) of reports of neutropenia were from combination of lapatinib with paclitaxel, which is known to be associated with neutropenia. All but 2 of the remaining reports occurred in studies where subjects received combination therapy with chemotherapeutic agents such as capecitabine, cisplatin, irinotecan, leucovorin or fluorouracil, all of which are associated with neutropenia.

Left ventricular ejection fraction (LVEF) has been evaluated using MUGA scans or echocardiograms (Echos) during lapatinib phase I, II and III trials. As of 22 June 2005 a total of 38 subjects on the lapatinib program have experienced a total of 39 events of decreased LVEF, giving an approximate incidence for this event of 1.3% [Perez, 2006]. The majority (65%) of decreases in ejection fraction were detected by week 8 of treatment, i.e. at the week 8 MUGA/Echo evaluation. Three events (two for one subject) remain blinded, and three subjects did not receive lapatinib. For the 33 subjects who received lapatinib, where outcome was reported, 10 events resolved or improved on discontinuation of lapatinib (as demonstrated by repeat MUGA/Echo), 8 events resolved or improved whilst lapatinib was continued, and 12 events were unresolved. For 3 events outcome was unknown at the time of reporting. Three of the 38 subjects with decreased LVEF presented with symptoms of breathlessness, dyspnoea, and signs of cardiac failure, and were found as part of their examination to have LVEF reduction. Two of these subjects had co-morbidities which could have contributed to the symptoms (one with pericardial and pleural effusions; one with diabetes, coronary artery disease, hypertension and hypercholesterolemia). The third subject had previously received trastuzumab. The events resolved on discontinuation of lapatinib and were assessed as lapatinib-related by the investigator. Thirty-two subjects were asymptomatic and the events were discovered on routine study MUGA/Echo examination. Twenty-four of these asymptomatic events were assessed by the investigator as related to treatment with lapatinib, 7 events were assessed as unrelated and 2 events had unknown causality at the time of reporting. Approximately half of the subjects in the lapatinib trials had previously received treatment with either anthracyclines and/or trastuzumab, both of which have been associated with cardiotoxicity. This exposure therefore increases the risk of cardiotoxicity in the lapatinib subjects irrespective of any cardiotoxicity attributed to lapatinib.

A more recent analysis of patients treated with lapatinib to date revealed that approximately 1.6% of patients in 43 studies had a decrease in LVEF. The frequency of symptomatic LVEF decrease was 0.2%. A sub-analysis performed in patients who had previously received an anthracycline-based therapy but no trastuzumab (Group 1, n=698), patients who previously received anthracycline-based therapy followed by trastuzumab (Group 2, n=  $\sim$ 700) and patients with mostly non-breast tumours who were treated with

neither anthracyclines or trastuzumab (Group 3, n=2200) indicated that there is a consistent frequency of LVEF decrease of approximately 1.4-1.6% and symptomatic events occurred at a frequency of 0.1 - 0.3%. The cardiac events were generally reversible and of short duration with a median of approximately 13 weeks. These encouraging results are in the process of being confirmed. (GSK data on File).

As of 04 December 2005, nine pulmonary events have been reported: five subjects experienced interstitial lung disease and four subjects experienced pneumonitis. Given current enrolment of 3876 subjects in the lapatinib program, this gives an approximate incidence of 0.2% for 'pneumonitis-type' events. Six subjects were participating in combination studies and one of these subjects did not receive lapatinib. The remaining three reports were from lapatinib monotherapy studies. Five subjects (55%) who experienced pulmonary events recovered. Three of these five subjects required treatment, commonly methylprednisolone or prednisolone. For the remaining four subjects, two events were fatal, one event was ongoing at the time of the subject's death due to disease progression, and one event was ongoing at the time of reporting.

As part of ongoing pharmacovigilance by GlaxoSmithKline, a review of all hepatobiliary events reported across the entire lapatinib clinical development programme has been performed. Two hundred sixteen reports of hepatic events were retrieved from the GSK safety database as of 31 December 2007 regardless of source (clinical trials, spontaneous/marketed use data). In 39 of the 216 cases, a causal association to lapatinib could not be ruled out: 38.5% (15/39) of these subjects received lapatinib monotherapy, 53.8% (21/39) of subjects received lapatinib in combination with other chemotherapies, such as capecitabine, and 3 cases were still blinded.

A total of 13 deaths were identified which contained hepatobiliary events. In 3 of these cases, an association with lapatinib could not be excluded. The remaining 10 cases were confounded by the patients underlying condition (progressive disease and/or progression of pre-existing liver metastases).

Based on an additional sub-analysis, of 18 clinical studies of lapatinib in breast cancer, using Hy's Law (defined as AST or ALT >3 x ULN, and total bilirubin >2 x ULN, with no initial findings of cholestasis i.e.: ALP <2 x ULN) as a predictor for potential drug induced liver injury, the liver injury associated with lapatinib seems to be the result of a prolonged exposure to the drug. All the subjects whose events potentially met Hy's Law received study medication for three months or longer. The majority of these cases appeared reversible. Most patients experienced a decline in liver enzymes with drug cessation.

Based on the results of this review, GSK concluded a causal relationship between hepatobiliary disorders (specifically transaminase elevations) and lapatinib cannot be excluded. As a consequence, hepatotoxicity was added to the core safety information (CSI) for lapatinib. In addition, for ongoing clinical trials, the monitoring interval for hepatic function has been increased to every 4-6 weeks during treatment, and stopping rules have been added for severe hepatic events. Lapatinib dosing should be discontinued if changes in liver function are severe and patients should not be retreated.

## 2.2.1. Rationale for Starting Dose in Monotherapy

Results from phase I studies support the use of 1500 mg po daily as achieving biologically active concentrations and target pathway inhibition with an acceptable toxicity profile.

Based on pre-clinical and phase I data, [Blackwell, 2005; Burnstein, 2005] performed two phase II trials in trastuzumab-refractory metastatic breast cancer. The primary objectives of these studies were the assessment of safety and efficacy of lapatinib monotherapy at the dose of 1500 mg daily. Preliminary side-effect data included events of rash, diarrhea, anorexia, nausea, vomiting and weight loss. Study drug-related adverse events were all grades 1-2 except for one grade 3 rash.

In this patient population lapatinib administered orally at 1500 mg daily provided evidence of efficacy with a clinical benefit rate of 22%. The results of these trials suggest activity of lapatinib in trastuzumab-pretreated patients.

Gomez HL et al. conducted a phase II randomized study of lapatinib as first-line treatment for patient with HER-2 FISH-amplified metastatic breast cancer. One hundred and thirty-eight patients were randomly assigned to receive lapatinib 1500 mg as a single daily dose (QD) or 500 mg twice daily (BID). A total of 138 patients were treated with lapatinib for a median of 17.6 weeks. The overall response rate (complete response [CR] plus partial response [PR]) was 24% in the intent-to-treat population, and 31% of patients derived clinical benefit (CR, PR, or stable disease for \_ 24 weeks). The median time to response was 7.9 weeks, and the progression-free survival rates at 4 and 6 months were 63% and 43%, respectively. The most common lapatinib-related adverse events (AEs) were diarrhea, rash, pruritus, and nausea, and these events were primarily grade 1 or 2. There were no significant differences in clinical activity or the AE profile between the dosing schedules. The authors concluded that lapatinib appeared well tolerated and showed evidence of activity as first-line treatment for women with HER-2 amplified advanced breast cancer [Gomez, 2008].

Furthermore, in study EGF 100151, a Phase III trial evaluating treatment with capecitabine alone or in combination with lapatinib in 324 patients with HER2-positive, locally advanced or MBC refractory to trastuzumab, the median time to progression (TTP) of patients in the combination arm (oral lapatinib 1250 mg QD plus capecitabine 2000 mg/m2/day on days 1–14 every 3 weeks) was significantly higher than that in the group receiving capecitabine alone (2500 mg/m2/day on days 1–14 every 3 weeks); median TTP of 36.9 weeks with combination therapy vs 19.7 weeks with monotherapy (p < 0.001, HR = 0.51, CI = 0.35–0.74) [Geyer, 2006].

Based on presented data this study hypothesizes that approximately 25% of patients with HER-2 non-amplified primary breast cancer acquire a HER-2 amplified *status* in the metastatic setting, particularly after treatment with systemic therapies for advanced disease. This multicenter phase II clinical trial attempts to demonstrate that a simultaneous inhibition of ErbB2 and ErbB1 is clinically active in advanced breast cancer patients with HER-2 positive or EGFR positive CTCs and HER-2 non-amplified primary tumours.

## 3. OBJECTIVE(S)

## 3.1. Primary Objective

The primary objective of this study is to evaluate the efficacy of a daily dose of lapatinib in advanced breast cancer patients with HER-2 non-amplified primary tumours with HER-2 or EGFR positive circulating tumour cells.

## 3.2. Secondary Objectives

The secondary objectives of this study are as follows:

- To evaluate antitumour activitiy of lapatinib
- To evaluate the safety of lapatinib
- To determine the early response of lapatinib on proliferation and the MAP kinase cascade by PET in a substudy in patients with EGFR positive CTCs only.

## 3.3. Translational Research Objective

The translational research objective is to correlate response to lapatinib with HER-2 and EGFR protein levels and amplification evaluated on CTCs before starting treatment. A centralized review of the HER-2 status on the primary tumour will retrospectively be performed.

## 4. ENDPOINTS

## 4.1. **Primary Endpoint**

The primary endpoint for the analysis is to evaluate the overall response rate (ORR) according to RECIST criteria.

## 4.2. Secondary Endpoints

The secondary efficacy endpoints are:

- Clinical Benefit Rate (CBR =  $CR+PR+SD \ge 24$  weeks)
- Duration of response (DoR) and of Clinical Benefit (DoCB)
- Time to Tumour Progression (TTP)
- Time to Best Response (TBR)
- Effects of lapatinib on tumour proliferation and MAP kinase activity in a subset of patients with EGFR positive CTCs as demonstrated on PET scan (Stratum 2 only)

The secondary safety endpoints are:

• Laboratory and non-laboratory toxicity

Safety will be measured using adverse events

## 4.3. Translational Research Endpoints

The translational research endpoints are:

- Evaluation of biological effects of lapatinib on EGFR and HER-2 in circulating tumor cells (CTC)
- Comparison between CTC and tumor samples from the primary and/or from the metastatic site in terms of biological marker expression profiles
- Correlation between EGFR both total and phosphorylated baseline levels evaluated on CTC before starting treatment and response to Lapatinib

## 5. INVESTIGATIONAL PLAN

## 5.1. Study Design

This study will be a multicenter open-label, phase II study to evaluate the efficacy and safety of daily dose of lapatinib in advanced breast cancer patients with HER-2 non amplified primary tumours. The patients will be allocated into one of the following two strata:

Stratum 1: Italian Study Group: Advanced breast cancer patients with HER-2 nonamplified primary tumours and HER-2 positive circulating tumour cells

Stratum 2: UK Study Group: Advanced breast cancer patients with HER-2 non-amplified primary tumours and EGFR positive circulating tumour cells.

The study will be conducted at approximately 15 centres in two countries, Italy and the UK. The HER-2 positive CTCs will be tested by the Italian group and EGFR CTCs will be tested by the UK group.

Patients enrolled in this study will be treated with oral lapatinib at the dose of 1500 mg daily on day 1 to 28 every 4 weeks (q 4 weeks).

Assigned therapy will be dispensed to the patient on day 1 after it has been confirmed that the patient meets all eligibility criteria and all screening assessments have been completed and the results reviewed. Patients enrolled in the study will return to the site every 4 weeks for additional supplies of lapatinib.

Treatment will be continued until disease progression, unacceptable toxicity or death whichever occurs first.

#### GM2007/00215/03

#### CONFIDENTIAL

Patients will carefully be instructed on drug administration as far as lapatinib oral intake is concerned. A daily dose of lapatinib is six 250 mg tablets taken approximately at the same time each day. Lapatinib must be taken either either at least 1 hour before or after meal.

Dose adjustment, modification and delays are permitted according to procedures described in Section 7.3.

If vomiting occurs after lapatinib intake, the patient should be instructed not to retake the dose. If vomiting persists, then the patient should contact the investigator.

The study will consist of three study periods: (I) screening; (II) treatment and (III) follow-up.

#### 1. Screening Period:

The screening period will include time from the timepoint in which eligible subjects sign the informed consent form until confirmation of eligibility from central laboratory based on CTCs ErbB1 and ErbB2 status. The screening phase can last up to 28 days prior to 1st dose.

[figure not shown]
#### 2. Treatment Period:

[figure not shown]
The treatment period will start from the 1st study drug dose intake until disease progression, unacceptable toxicity or death whichever occurs first.

#### 3. Follow up Period:

This period will commence 28 days from the time of last study drug dose intake. Poststudy survival follow up status will be collected every 12 weeks and can be collected by phone if the patient cannot attend the hospital.

This study is also designed to examine the early effects of lapatinib on tumour proliferation and MAP kinase activity using PET. This sub-study will only be conducted in the UK centre. Patients must satisfy the additional eligibility criteria in order to enter this sub-study. The PET sub-study is outlined in Appendix 4.

\*\*PET sub-study will only be performed on paitents with EGFR positive CTCs who have met the additional entry criteria, see Appendix 4 for details.

\*\*\*Central laboratory: Translational lab at Prato Hospital for Italian Study Group and Hammersmith Hospital for the UK Study Group

Supplementary study conduct information not mandated to be present in this protocol is provided in the Appendix 3.

## 6. SUBJECT SELECTION AND WITHDRAWAL CRITERIA

## 6.1. Strata

The subjects will be allocated into one of the following two strata:

Stratum 1) Italian study group: Advanced breast cancer patients with HER-2 nonamplified primary tumours and HER-2 positive circulating tumour cells

Stratum 2) UK study group: Advanced breast cancer patients with HER-2 non-amplified primary tumours and EGFR positive circulating tumour cells.

## 6.2. Number of Subjects

The study is designed as a two-stage three-outcome phase II trial in each stratum.

## 1st Stage:

Initially 16 eligible subjects in each stratum will be treated, and

- if no response is observed, the drug will be declared to be insufficiently active
- if 4 or more responses are observed, the drug will be declared to be sufficiently active
- if 1 to 3 responses are observed, study will proceed to the second stage as follows.

## 2nd Stage:

Treat up to 15 additional subjects in each stratum (up to 62 patients in total), and

- if up to 2 responses in total are observed, the drug will be declared to be insufficiently active
- if 4 or more responses in total are observed, the drug will be declared to be sufficiently active
- if 3 responses in total are observed, no final conclusion can be drawn from this study

Note that after accrual of 16 subjects in each stratum, the trial can terminate as soon as 4 responses are observed in that stratum. It is considered lapatinib has sufficient activity in the target population that when 4 or more responses are observed because it is expected that lapatinib should have no activity in HER-2 negative breast tumour.

## 6.3. Inclusion Criteria

This study attempts to prove the concept that patients who would never be treated with anti-Her-2 compounds can indeed be considered for this option. Specific information regarding warnings, precautions, contraindications, adverse events, and other pertinent

information on the investigational product that may impact subject eligibility is provided in the latest version of the lapatinib Investigator's Brochure or product labels.

Subjects eligible for enrolment in the study must meet all of the following criteria:

- 1. Signed written informed consent
- 2. Female patients, age  $\geq 18$  years
- 3. Histologically confirmed diagnosis of HER-2 negative (i.e. no gene amplification by FISH or IHC 2+ and no amplification by FISH or IHC 0/1+) infiltrating primary breast cancer.
- 4. Evidence of EGFR positive circulating tumour cells or HER-2 positive (≥50% CTCs or FISH positive) in a peripheral blood sample taken at screening visit.
- 5. Metastatic disease with at least one measurable lesion as per RECIST criteria classification [Therasse, 2000]
- 6. No brain metastasis requiring local therapy. Stable or asymptomatic subjects are allowed.
- 7. Availability of tumour block or at least six unstained 4  $\mu$  sections of the primary tumour to be sent to the central lab after eligibility confirmation for HER-2 central testing by FISH.
- 8. Eastern Cooperative Oncology Group (ECOG) score for performance status 0 to 3 (Appendix 1)
- 9. Life expectancy > 12 weeks
- 10. Adequate baseline organ function at screening visit:
  - Hematologic function:
    - ANC  $\geq$  1,000 / mm^3,
    - PLT  $\geq$  100,000 / mm^3,
    - $Hb \ge 10g / dL$  (after transfusion if needed)
  - Hepatic function:
    - GOT/GPT/alkaline phosphatase ≤ 3 ULN without liver metastases or ≤ 5 ULN if documented liver metastases;
    - total bilirubin: ≤1.5 ULN unless due to Gilbert's syndrome
  - Renal function:
    - serum creatinine ≤ 2.0mg/dL or Calculated Creatinine Clearance ≥ 25mL/min (Appendix 2)
- 11. Normal left ventricular ejection fraction (LVEF) by echocardiogram or MUGA.
- 12. Negative serum pregnancy test (only in childbearing potential female)
- 13. Patients with reproductive potential needs consistent and correct use of adequate non-hormonal methods of birth control (barrier methods or intrauterine device)

- 14. Previous treatment with anthracyclines and/or taxanes in the neo-adjuvant, adjuvant or advanced setting
- 15. At least one line of treatment for metastatic disease

Refer to Appendix 4 for additional inclusion criteria for patients who participate in the PET sub-study.

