#### 8.3.1.1. Measurability of Tumour Lesions at Baseline

All measurements should be recorded in metric notation, using a ruler or calipers. All identified tumour lesions are to be classified as measurable or non-measurable per RECIST criteria [Therasse, 2000].

**Measurable lesions:** lesions that can be accurately measured in at least one dimension with the longest diameter  $\ge 20$  mm using conventional techniques, or  $\ge 10$  mm with spiral CT scan.

**Non-measurable lesions:** all other lesions, including lesions too small to be considered measurable (longest diameter < 20 mm using conventional techniques or < 10 mm with spiral CT scan), and the following lesions and disease sites: bone lesions, ascites, pleural/pericardial effusions, lymphangitis cutis/pulmonis, and cystic lesions.

**Measurable disease:** subjects presenting with at least one measurable lesion at baseline are identified as having **measurable disease.** 

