#### 8.3.1.2. Determination of Target Lesion

At baseline, all the lesions must also be categorized as "Target" or "non-Target" lesions using the following RECIST guideline.

**Target lesions:** all measurable lesions up to a maximum of five lesions per organ and 10 lesions in total, representative of all involved organs should be identified as *target lesions*, and measured and recorded at baseline.

Target lesions should be selected on the basis of their size (lesions with the longest diameter) and their suitability for accurate repeated measurements (either by imaging techniques or clinically). Lesions that are present within a previously irradiated area cannot be selected as target lesions.

**Non-target lesions:** all other lesions (or sites of disease) should be identified as non-target lesions, and should also be recorded at baseline. Measurements of these lesions are not required, but the presence or absence of each should be noted throughout subsequent assessments.

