#### 8.3.1.3. Response Evaluation of Measurable Disease

A sum of the longest diameter (LD) for all target lesions will be calculated and reported as the baseline sum LD. The baseline sum LD will be used as reference by which to characterize the overall tumour response. During Treatment Assessments, any new lesion(s) must be recorded in the CRF. If the lesion(s) noted at baseline is not evaluated at the subsequent Treatment Assessment, this will be noted as 'not done' (ND) in the CRF.

RECIST Response criteria for target and non-target lesion(s) are presented in Table 9.

Evaluation of Target Lesions				
Complete response (CR)	Disappearance of all target lesions			
Partial response (PR)	At least a 30% decrease in the sum of the LD of target lesions, taking as a reference the baseline sum LD			
Progressive disease (PD)	At least a 20% increase in the sum of the LD of target lesions, taking as a reference the smallest sum LD recorded since the treatment started or the appearance of one or more new lesions			
Stable disease (SD)	Neither sufficient shrinkage to qualify for PR nor sufficient increase to qualify for PD, taking as reference the smallest sum LD since the treatment started			
Not evaluable (NE)	Any subject who cannot be classified by one of the four preceding definitions			
Evaluation of non-Target Lesion	S			
Complete response (CR)	The disappearance of all non-target lesions			
Incomplete response/Stable Disease (SD)	The persistence of one or more non-target lesion(s)			
Progressive disease (PD)	The appearance of one or more new lesions and/or unequivocal progression of existing non-target lesions			

Table 9	RECIST Response Criteria for Target and non-Target L	esions
---------	--	--------

New bone scan lesions that are equivocal will be considered as new malignant lesions if a confirmatory assessment using X-ray, CT or MRI is not available, and the subject will be determined as having progressive disease.

If a bone assessment is missing at baseline, any new bone lesions identified after the first dose that is either consistent with or equivocal for tumour metastasis will be considered as new bone (malignant) lesions and the subject will be considered as having progressive disease.

The best overall response is the best response recorded from the start of the treatment until disease progression/recurrence (taking as reference for PD the smallest measurements recorded since the treatment started).

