Table 10 shows the overall response for all possible combinations of tumour responses in target and non-target lesions, with or without the appearance of new lesions.

Target Lesions	Non-Target Lesions	New Lesions	Overall Response
CR	CR	No	CR
CR	Incomplete response/SD	No	PR
PR	Non-PD	No	PR
SD	Non-PD	No	SD
PD	Any	Yes or No	PD
Any	PD	Yes or No	PD
Any	Any	Yes	PD

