# 11.3. Data Analysis Considerations

# 11.3.1. Analysis Populations

## **Per Protocol Population**

The per protocol population will be defined as all subject fulfilling major entry inclusion/exclusion criteria who received at least 75 % of study drug doses up to first tumour assessment at week 12, and have at least one efficacy measurement available on the primary outcome. Subjects who progress prior to the week 12 assessment will also be included in this analysis. This population will be used for the primary objective of the study and for all efficacy analyses and summaries.

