## 11.4. Interim Analysis

An interim analysis will be performed as soon as 16 eligible subjects can be evaluated for response. The study recruitment will continue beyond 16 subjects until tumour response can be evaluated on the first 16 subjects.

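### Inclusion 5 accepts a patient whose only measurable lesion was previously irradiated, yet 8.3.1.2 bars that lesion as a target, so she can never be scored a responder

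*Protocol*

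**What the plan says.** **Eligibility.** Section 6.3, criterion 5, asks for "Metastatic disease with at least one measurable lesion as per RECIST criteria classification". Prior radiotherapy is not mentioned there. In 6.4 only exclusion 8 deals with radiotherapy, and it covers concurrent treatment only.

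**Measurability.** Section 8.3.1.1 counts as measurable "lesions that can be accurately measured in at least one dimension with the longest diameter" at or above 20 mm by conventional techniques or 10 mm by spiral CT. The non-measurable group holds lesions that are too small, bone lesions, ascites, effusions, lymphangitis and cystic lesions. Irradiated lesions are not named. One measurable lesion is enough for measurable disease.

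**Targets.** Section 8.3.1.2 then adds: "Lesions that are present within a previously irradiated area cannot be selected as target lesions".

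**Scoring.** In Table 9, partial response is "At least a 30% decrease in the sum of the LD of target lesions", and stable disease is defined on the same sum. Not evaluable is "Any subject who cannot be classified by one of the four preceding definitions". Table 10 is presented as giving the "overall response for all possible combinations of tumour responses in target and non-target lesions".

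**Analysis.** Section 11.5.1 keeps subjects with unknown or missing response in the denominator as non-responders. The per-protocol population of 11.3.1, used for the primary objective, includes subjects who "have at least one efficacy measurement available on the primary outcome" and also those who progress before week 12. Section 11.4 states: "An interim analysis will be performed as soon as 16 eligible subjects can be evaluated for response".

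**The concern.** The eligibility test (measurable) is wider than the test for being assessable on the primary endpoint (has a target lesion). A patient can pass the first and fail the second. She would receive lapatinib in a trial whose primary endpoint cannot register a benefit to her.

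For the stratum, she either enters the response rate with no possibility of counting as a response, or drops out of the per-protocol set and leaves it one patient smaller; 6.5 does not replace subjects who discontinue early. Both outcomes push the decision rule slightly towards rejecting an active drug. Single responses matter in this rule: a final total of 2 rejects, 3 is inconclusive and 4 accepts.

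**Working it through.** **Step 1. Follow the patient through the text.** Her only measurable lesion was irradiated before entry.

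| Question | Source | Answer |
|---|---|---|
| Is the lesion measurable? | 8.3.1.1 | Yes, if large enough |
| Does she meet the disease criterion? | 6.3, criterion 5 | Yes |
| Does an exclusion name prior radiotherapy? | 6.4 | No |
| Can the lesion be a target? | 8.3.1.2 | No |
| Is there a baseline sum of diameters? | 8.3.1.3 | No, there is nothing to sum |
| Which Table 10 rows can apply? | Table 10 | Only non-target progression or a new lesion, both giving PD |
| Otherwise? | Table 9 | Not evaluable |

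Every CR, PR and SD row of Table 10 starts from a target-lesion result of CR, PR or SD. If all her disease disappeared, no row would record it.

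**Step 2. Reproduce the design.** Inputs from 11.1 and 11.2.1: response rates 5% and 20%; n1 = 16; n2 = 15; reject at 0 responses in stage 1 or at most 2 in total; accept at 4 or more at either stage; inconclusive at 3 in total. With X ~ Bin(n1, p) and Y ~ Bin(n2, p):

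- P(reject) = P(X=0) + P(X=1)·P(Y≤1) + P(X=2)·P(Y=0)
- P(inconclusive) = P(X=1)·P(Y=2) + P(X=2)·P(Y=1) + P(X=3)·P(Y=0)
- P(accept) = 1 − P(reject) − P(inconclusive)

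At p = 0.20:

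- P(reject) = 0.0281 + 0.1126 × 0.1671 + 0.2111 × 0.0352 = 0.054
- P(inconclusive) = 0.1126 × 0.2309 + 0.2111 × 0.1319 + 0.2463 × 0.0352 = 0.063
- P(accept) = 0.883

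At p = 0.05 the same formulas give accept 6.5%, reject 81.5% and inconclusive 12.0%. The protocol sets α at 10%, β at 5% and correct decisions at 80% or more. The design therefore reproduces, with β at 5.4%, slightly above its nominal 5%.

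**Step 3. Add patients who cannot respond.** Their number is an assumption, because the protocol gives none. A certain non-responder in a stage has the same effect as reducing that stage's n by one with the cut-offs unchanged. There are two cases:

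- She uses a stage 1 place. Section 11.2.1 counts treated eligible subjects, or she progresses and so is evaluable under 11.4.
- Section 11.4 is read as keeping 16 evaluable subjects in stage 1, and only stage 2 loses a place.

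| Case (p = 0.20) | Effective n | Accept | Reject | Inconclusive |
|---|---|---|---|---|
| As designed | 16 + 15 | 88.3% | 5.4% | 6.3% |
| One, stage 1 | 15 + 15 | 86.5% | 6.5% | 7.0% |
| One, stage 2 only | 16 + 14 | 86.9% | 6.0% | 7.1% |
| Two, stage 1 | 14 + 15 | 84.4% | 7.9% | 7.7% |
| Two, stage 2 only | 16 + 13 | 85.3% | 6.6% | 8.1% |

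One such patient costs 1.4 to 1.8 points of acceptance (88.3 − 86.9 and 88.3 − 86.5).

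**The case against.** **The protocol presupposes a target lesion.** Section 8.3.1.2 draws targets from the measurable lesions, exclusion 8 speaks of the only target lesion, and 8.3.1.3 takes the baseline target sum as the reference. A sensible investigator might therefore read criterion 5 as meaning a lesion usable as a target. That reading is reasonable, but it is an inference: no eligibility sentence states it, and eligibility is decided on the sentence.

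**The cited RECIST publication may settle it.** Criterion 5 and 8.3.1.1 both refer to it, and it was not consulted here. What can be said is that the protocol's own restatement puts the irradiation rule under target selection, not under measurability or eligibility.

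**The stage 1 figures overstate the cost.** This stands. A patient who progresses through a new lesion or non-target disease is PD under Table 10 whatever her target status, so that result is a real failure on treatment and not a scoring artefact. If she does not progress, 11.4 may keep her out of the stage 1 count and 11.3.1 may remove her from the primary population. The stage 1 rows are a worst case.

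**A stronger reading about exclusion 8.** A reader might infer that exclusion 8 also needs rewriting, because it bars concurrent radiotherapy only to the sole target while 7.9.2 bars it on target lesions generally. The documents do not support a change. Section 7.9.2 already prohibits radiotherapy on target lesions during treatment (adjuvant exception aside). Section 7.9.1 confines permitted radiotherapy to non-target bone lesions before enrolment. And a lesion already in a radiation field at baseline arguably cannot be a target under 8.3.1.2.

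**Conclusion.** The gap is real and follows from the current text: criterion 5 can admit a patient who cannot be scored CR, PR or SD. Its expected effect is small. With one such patient per stratum, acceptance at a 20% response rate moves from 88.3% to 86.5–86.9% and false rejection from 5.4% to 6.0–6.5%. With two, acceptance is still at least 84.4%. These figures assume a true rate of 20% in the remaining patients, unchanged cut-offs and an assumed count.

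Two larger claims might be inferred and should not be made:

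- **That the design loses its planned 80% acceptance.** If a share f of patients cannot respond, the effective rate is 0.20 × (1 − f). At f = 10% acceptance is 82.3%. It falls below 80% only near f = 15% (rate 17%: accept 78.5%, reject 10.8%), and the protocol gives no basis for a share that high.
- **That the gap causes the 5% false-rejection limit to be missed.** The rule gives 5.4% before any such patient is enrolled; the gap only adds to it.

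This is a cheap improvement to the eligibility wording, not a redesign. It belongs in the protocol because eligibility is fixed there.

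**What to change.** Reword 6.3, criterion 5, to require metastatic disease with *at least one measurable lesion that qualifies as a target lesion under 8.3.1.2 (not in a previously irradiated area)*. Leave exclusion 8 as it is.

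The sample size, decision rule, Tables 9 and 10 and assessment schedule do not change, and no procedure is added. The 88.3% and 5.4% of the design as written are then no longer eroded by this route. The cost is that a few patients whose only measurable disease was irradiated become ineligible.
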